1. RISKS TO THE SUBJECTS

a. Human Subjects Involvement and Characteristics

In Phase 1, two Adolescent Advisory Boards (AABs) composed of 8 members each will be convened in Rhode Island. A Health Education Professionals Panel (HEPP) of 8 school professionals will also be formed to advise on the translation.

In Phase 2, sixteen participants will take part in the Acceptability Testing Phase to complete the intervention and assessment to test procedures for the RCT. One hundred twenty adolescents (ages 12-14) and their parents will be recruited from public middle schools in Rhode Island for the Randomized Controlled Trial Phase.

For both phases, Inclusion criteria: enrolled at a participating school, in the 7th grade, between the ages of 12 and 14 years, and has a parent/legal guardian who speaks English or Spanish to provide consent. Exclusion criteria: unable to read English at a 4th grade level, has a sibling who has participated in the project, or has observable cognitive or developmental delays that would preclude participation. In the RCT, eligible adolescents will be randomized to participation in a web-based, tablet-delivered emotion regulation intervention (iTRAC-SRP) or a waitlist control until the goal of 120 participants is reached. Adolescents will be recruited from four schools in the Cranston School District: Hope Highlands Middle School, Bain Middle School, Western Hills Middle School, and Park View Middle School. (See **Resources** for more information on sites).

Students will be introduced via a brief description of the program emphasizing the content (sexual and emotional health) and approach (gaming), both of which are of interest to this age group. The introductions will be conducted by project staff in small groups (e.g., homerooms), who will distribute flyers with “consent to contact” forms for parents to sign and return. Principals will introduce the project via emails sent to all parents with school announcements. A REDCap link to the consent to contact form is attached for parents to complete electronically, to avoid students having to remember to return the form. Project staff will also recruit at school events attended by parents (open houses, sporting events, etc.).

Once permission to contact the family has been received, school staff involvement ends (to avoid perceived pressure to participate). Trained research staff will contact parents to arrange an individual meeting to describe the project activities they are being asked to complete and obtain parental consent. Participants will be compensated for their time and effort. Staff will separately explain the project to adolescents and obtain assent away from their parent's presence.

These procedures will be used for both Phase 1 and Phase 2. Fewer homerooms will need to be approached for the Translation and Acceptability stages, as fewer participants are needed.

A Health Education Professionals Panel of school personnel key to student health will also be formed to advise on the adaptation of the intervention to digital format. Identified from throughout the school system, this will include individuals with involvement in student health and risk behaviors (e.g., health teachers, administrators, school counselors, school nurses). Once each pool of professionals from Cranston Public Schools is identified, individuals within each profession will be chosen at random, to ensure a mix of perspectives are represented in the HEPP. They will be contacted using their publicly available school email addresses and offered participation. Additionally, members of the Rhode Island Department of Health (RIDOH) school nurses listserv, as well

as representatives from the Planned Parenthood Federation of America, will be contacted and encouraged to outreach study staff if interested in participating.

Adolescent participation for all activities will require parent consent and adolescent assent. Adolescents and their parents will be agreeing to let us use adolescent feedback as data for program adaptation and development in the Translation and Acceptability Testing stages. In the RCT stage, adolescents and their parents will be agreeing to the adolescent's participation in an 8-module tablet-delivered health intervention and completion of computerized questionnaires at three points (baseline, 2-, and 6-month follow-ups). Similarly, parents will provide responses to questionnaires. They will be agreeing to let their responses, collapsed with those of other participants, be used for reporting scientific results. Adolescents and their parents will be assured that they are free to withdraw from the study at any time.

For all phases, once permission to contact the family has been received, trained research staff will contact parents to introduce and describe the program and what it involves for parents and teens. At the conclusion of this conversation, parents will be asked whether they would be interested in meeting to learn more about the program. Research staff will then arrange an individual meeting at a location convenient to them (e.g., the research office, the school, home, etc.) to describe the project in detail, obtain parental consent, and (for the RCT Phase) complete measures, for which they will be compensated for their time and effort. Separate meetings for adolescents will be arranged (typically at the school) to explain the project and obtain assent away from their parent's presence. Adolescents will be reassured that they do not have to participate in the program despite their parent's consent. They will be told that if they do not wish to participate, the research staff will not disclose to parents the reason that the student is considered ineligible, in order to protect their privacy and avoid coercion to participate. These methods have been successful in recruiting and consenting eligible adolescents in our previous projects.

b. Sources of Materials

Participants in the Translation Stage (Phase 1) will provide feedback through discussions (AAB focus groups). Study staff will take notes on feedback provided by the Adolescent Advisory Boards. Data collected during this stage will include de-identified written notes taken by the research team during the meetings. During focus groups, discussions will be audiorecorded.

Participants in the Acceptability Testing Stage (Phase 2) will complete brief questionnaires assessing acceptability and usability after each module and participate in interviews about their experience with the digital modules (e.g., learning process, etc.). These discussions will be audiorecorded as well. They will also complete self-report questionnaires and computerized tasks to test assessment procedures for the RCT.

Participants in the Randomized Trial (Phase 2) will complete audio computer-assisted self-interviews (ACASI) on laptops at baseline, 2-, and 6-months after baseline. Adolescents will complete several questionnaires assessing demographic information, sexual attitudes and cognitions, risk behaviors, and emotional functioning. Parents will complete a locator form to assist in retention and tracking, as well as measures of demographic information and their adolescent's emotion regulation. Teens will also complete performance measures related to emotion regulation (Behavioral Indicator of Resilience to Distress; Diagnostic Analysis of Nonverbal Accuracy-2).

c. Potential Risks

The risks in this study are considered minimal. During the Translation phase, participation requires only attendance at Advisory Board meetings where opinions will be shared, though participants will be advised that they may decline to answer any questions at any time. During Acceptability Testing, participation requires completion of the web-based program across several sessions, and completion of measures and interviews that assess the acceptability and clarity of the web-based program. Similarly, during the RCT, participation requires completion of measures as described above and participation in the finalized web-based program.

Some adolescents and parents may feel uncomfortable with the topics regarding sexual health. Families are notified of this content during the informed consent process. These topics will be discussed sensitively and openly, in a developmentally appropriate way during all phases of the project. Moderators during feedback

sessions will be trained to help participants with topics of sex and sexuality. In addition, they will heavily encourage confidentiality and respect.

With respect to use of the ACASI for data collection, the computer-assisted format is expected to reduce participants' discomfort answering questions about sensitive topics such as sexuality because the computer assessment format will prevent others from becoming aware of adolescents' answers. However, it will also be emphasized to participants that they may skip anxiety-provoking questions on any survey and that they can terminate their participation at any time during the course of data collection or interventions. If at any point during data collection or during the intervention, a parent or adolescent wishes to discontinue participation, they will be allowed to withdraw from the study without negative consequences.

While not directly assessed during the intervention or assessment procedures, if a subject discloses an abusive experience to project staff, parents will be notified and the matter resolved in accordance with standard hospital clinical practice (see **Protection Against Risks**). A similar protocol (described below) will be followed if adolescents disclose suicidal or homicidal ideation during the study.

2. ADEQUACY OF PROTECTION AGAINST RISKS

a. Informed Consent and Assent

Only research staff at Rhode Island Hospital will consent participants. Given that our study involves children, we have carefully designed our consent and assent procedures to meet HHS regulatory requirements for parental permission and child assent (45 CFR 46.408). Specifically, trained project staff will gather informed consent/assent from all participants in person. Parents will provide informed consent for their adolescent and their own participation in the project. Adolescents will provide assent for participation. Staff members will inform the parent of the research study procedures, discuss the inherent risks, explain the rules of confidentiality and obtain consent. Separate from parents, staff members will individually speak with each adolescent to describe the study procedures, review the inherent risks, discuss the rules of confidentiality and obtain assent. Research staff will be available to answer any questions about the study. All signed consent forms will be locked away securely and kept separate from any study data (see below). Participants will be provided with copies of the Informed Consent/Assent Forms.

b. Protection Against Risk

As noted above, participation in all phases of the project is entirely voluntary and participants are free to withdraw from the project at any time, without negative consequences to their affiliation with the referring school.

Confidentiality. The study will maintain confidentiality of stored records according to the following guidelines:

- All records will be kept by assigned study numbers;
- RIH will maintain locked files of all gathered data and permit access only to authorized individuals. (The schools and any associated staff members will not have any access to these records.);
- Completed, signed consent forms will be stored in a separate, locked cabinet that holds no other study information;
- Data collected on laptops will be downloaded after each assessment onto a flash drive as separate password-protected files prior to transfer to RIH's secure servers; the flash drives will be stored in a locked cabinet at RIH;
- Audio files will be transferred from recording equipment to RIH encrypted servers and deleted from the original source. Any backup drives used will also be encrypted. Files will be deleted at the conclusion of the study;
- RIH will maintain a separate, secured digital file that holds the list linking study identification numbers to names. Only the Principal Investigator and the research assistants will have access to this list, which will be destroyed at the completion of the project;
- Notes and transcripts from focus groups will be deidentified and will be kept in locked cabinets;
- Conclusions and final results will be presented for aggregate data only, with no disclosure of specific cases;

- Collected information will not be released without the explicit consent of the participant, according to the Privacy Act;
- No personal identifying information will be released to NIH.
- All personal identifying information will be removed from data prior to sharing with Klein Buendel, Inc staff.

Backend user data during the Acceptability and RCT stages will be collected and stored via internet to Klein Buendel's server farm. KB's server farm has five Dell PowerEdge servers with two 3.2 Ghz Xeon processors, two with 32 gigabytes of RAM and two with 128 gigabytes, and three 1 Terabyte hard drives that operate off a hardware RAID5 system, connected to a local area network (LAN) running the Windows 2008 or 2012 operating system, and to the Internet through a 50 megabyte fiber connection. KB programmers monitor and maintain all programs and databases, working with data management staff. Sensitive information is protected by a hardware firewall (SonicWall TZ600) and each server has its own native Windows security software. All KB servers are connected via 1 Gigabit high-speed switched network, ensuring high-speed transfer between machines. All networked computers are protected from viruses by Sunbelt Vipre Business. A nightly backup of each computer provides protection against the loss of data.

Trauma-Informed Approach. Consistent with SAMHSA's Trauma-Informed Approach and guidelines published by CARDEA (Guide to Trauma Informed Sex Education) and the Responsible Sex Education Institute, iTRAC-SRP will be sensitive to the experiences of participants with a history of trauma. These focus on principles fundamental to a trauma-informed approach. While some recommendations apply to in-person, group-based education programs (collaboration and mutuality, peer support), many can be incorporated into technology-delivered platforms.

Safety, both physical and emotional, is the foundation for a trauma-informed approach to sexual health education. iTRAC-SRP has advantages in creating a safe environment that may not exist in some group-based programs. The content is standardized and avoids shaming language ("you shouldn't have sex..."). Participants may proceed at their own pace, maintaining control throughout the program. In addition, other participants are not present to introduce content that may lead to strong emotions based on their personal experiences. In this way, technology-delivered sex education may be a more effective strategy than classroom-based learning where some students may have undesired responses. **Trustworthiness and transparency** will be achieved by alerting participants to upcoming sexual health content before it is presented (e.g., drawings of sexual anatomy). These activities are also used as practice with emotion regulation, as they are emotionally arousing for most adolescents regardless of trauma history because of the taboo around sexual health in US culture. Thus, coaching will be provided for use of ER skills to manage feelings while learning this important content. These skills are expected to increase the likelihood that participants will recall the information provided and will increase self-efficacy for ER strategy use. **Empowerment and choice** are facilitated through the teaching of emotion regulation skills as a way to manage emotions that might otherwise influence decisions in ways that adolescents do not intend. Other strategies for creating empowerment include reaffirming bodily autonomy during all sexual health content- that they have many choices over what happens to their body and when- and allowing participants to skip questions that they prefer not to answer during assessment procedures. **Cultural, historical, and gender issues** will be considered in all elements of the program, to avoid stereotypes and biases. The use of a space theme allows for use of non-human characters that are not easily associated with cultural stereotypes. Of particular importance in sex education programs is consideration of heteronormative language that may exclude youth who identify as LGBTQ. Inclusive language (e.g., "partner" vs. "boyfriend/girlfriend") creates a safe environment for all participants and reflects sensitivity to the traumas experienced by many who have historically had less power in our culture.

The sexual health content of TRAC has been used in a previous large trial without adverse events. Staff will be provided education to improve awareness of how trauma can affect youth, families, and communities to inform their day-to-day work with participants. Descriptions of violence or abuse that might be particularly sensitive for those with trauma histories are not a part of the original TRAC program. Adolescents consistently see sexual content in media and social media; the content of iTRAC-SRP will be developmentally appropriate and provide a context in which adolescents can interpret the information that they receive in other forums. People with trauma histories can lead full lives and develop healthy sexual identities; sexual health education is critical to this development. Respectful, affirming programs are key to this process and can be achieved through

technology. Those that incorporate emotion regulation skills may be particularly valuable to those with trauma histories as they navigate sexual content and experiences in their lives.

If a subject discloses an abusive experience, suicidal, or homicidal thoughts and/or behavior during any phase of the project, a trained research staff member will interview the subject immediately and the PI will be contacted. Next, the parent will be notified and the matter resolved in accordance with standard medical/psychiatric care as follows. Abuse is a reportable condition. In the majority of cases, a history of abuse has already been reported to the appropriate authorities. If not previously disclosed, the situation will be reported to authorities per state law and hospital standards. Suicidal or homicidal thoughts or behavior will be handled in the same fashion and the case will be reviewed immediately with one of the investigators. If the participant is in imminent danger, the participant will be taken by ambulance to the nearest hospital emergency room for immediate intensive psychiatric evaluation. Participants are informed of the limits to confidentiality, including these reportable conditions, during the consent process.

c. Vulnerable Subjects

Our study is aimed at completing the development and testing the efficacy of a preventive intervention designed for middle schoolers. As such, this study necessitates the involvement of children. Importantly, this study presents **no greater than minimal risk** to children. Furthermore, as noted above, we have made numerous provisions for soliciting the assent of the children and the permission of their parents or guardians.

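### The abuse-disclosure procedure has the parent notified, with no stated exception when the person named is a parent or household member and no stated order relative to the report to authorities

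*Combined protocol and SAP*

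**What the plan says.** Two places in the Human Subjects part of the combined protocol and SAP cover a disclosure of abuse.

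Section 1.c (Potential Risks) says that "if a subject discloses an abusive experience to project staff, parents will be notified and the matter resolved in accordance with standard hospital clinical practice", and refers the reader on to the protections section.

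Section 2.b (Protection Against Risk), at the end of the text on the trauma-informed approach, gives the steps. They apply in every phase of the project. First, "a trained research staff member will interview the subject immediately and the PI will be contacted". Then: "Next, the parent will be notified and the matter resolved in accordance with standard medical/psychiatric care as follows". The text goes on to call abuse a reportable condition and adds: "If not previously disclosed, the situation will be reported to authorities per state law and hospital standards". On the other type of disclosure it says: "Suicidal or homicidal thoughts or behavior will be handled in the same fashion". It also provides for immediate case review with an investigator and for ambulance transfer to an emergency room if danger is imminent.

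**The concern.** The participants are 12 to 14 years old and the subject matter is sexual health. An adolescent who discloses abuse may be naming someone at home. A rule that the parent will be notified suits a disclosure about someone outside the household. Where the person named is the parent, or lives with the parent, the same rule would pass the child's words to that person or to someone close to them. If that happened before the authorities had the report, the child could face retaliation or pressure to retract before anyone could protect them.

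This is a participant-safety question, not a statistical one. It matters now because the procedure covers all phases, including Phase 1, the only phase for which approval is being sought.

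**Working it through.** No arithmetic applies. The check was to set the relevant sentences side by side and look for two things: a condition on parent notification, and a stated order of notification and report.

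**1. Trigger.** Section 2.b opens with any disclosure of an abusive experience, or of suicidal or homicidal thoughts or behavior. It does not ask who is named.

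**2. Notification.** Both sections say the parent *will* be notified. Each then refers to an outside standard (hospital clinical practice in 1.c, medical and psychiatric care in 2.b). In each sentence that reference most naturally attaches to how the matter is resolved, with notification as a separate step. Section 2.b then sets out the handling, and no exception appears in it.

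**3. Order.** The word that opens the notification sentence in 2.b places it after the interview and the contact with the PI. The report is described later, with no time limit and no statement of whether it comes before or after notification. A reader working down the page would probably tell the parent first, but the text does not say so.

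**4. Search for an exception elsewhere.**
- Consent: "Participants are informed of the limits to confidentiality, including these reportable conditions, during the consent process". This tells families that reporting can happen. As worded, it does not limit whom staff notify.
- Data and Safety Monitoring Plan: staff contact the PIs about any potentially adverse event, and the PIs investigate and decide how to proceed. The text does not mention abuse disclosures or parent notification.
- Trauma-informed approach: staff are to be educated about the effects of trauma. No rule on notification follows from that.

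**5. Two cases under the literal text.**

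| Person named | Steps as written | Result |
|---|---|---|
| Someone outside the household | Interview, PI contacted, parent notified; report made if not already made | Reasonable |
| Parent, guardian, household member or parent's partner | The same steps | The person named, or someone close to them, may be told, possibly before the report |

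The text gives staff no instruction that separates the second case from the first.

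**The case against.** The best case for the text as it stands has four parts.

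*The outside standards govern notification too.* The reference to hospital practice can be read as covering both verbs, so that notification itself follows those standards. They may well address an implicated caregiver. This partly stands: the standards are not in the file, so the finding is that the protocol states no safeguard, not that none exists.

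*The PI is contacted first and will use judgment.* This also partly stands. The contact comes before notification and softens any claim that the rule is mechanical. But no decision is assigned to the PI at that point, and no authority to withhold or delay notification is stated.

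*Cases will be few.* Abuse is not directly assessed, descriptions of abuse were not part of the original program, and the protocol says: "In the majority of cases, a history of abuse has already been reported to the appropriate authorities". This stands as to frequency. It does not answer the case of a new disclosure about someone at home.

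*How much hospital procedure to restate is a drafting choice.* That would be fair if the protocol were silent. Here it states a specific step that could be harmful if followed.

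A reader might infer more than the documents support: that the protocol orders notification before the report, that it conflicts with state law or hospital policy, or that the PI has no discretion. The order is left unstated, the law and policies are not in the file, and the PI's role at that step is simply not described.

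**Conclusion.** The concern holds in a limited form. The protocol states that the parent will be notified after an abuse disclosure. It gives no exception for an implicated parent, guardian, household member or parent's partner, and does not place notification relative to the report. Followed literally, that step could inform the person named before a report is made.

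Its size cannot be put as a number, because the documents give no disclosure rate and none is assumed here. The weight comes from the severity of a single event. Sample size, power and the analysis are untouched.

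The conclusion rests on two readings: that the deferral to outside standards governs resolution rather than notification, and that the adverse-event text in the Data and Safety Monitoring Plan was not written for this situation. If the hospital standards do contain a safeguard, the remaining problem is that the protocol's own wording does not point staff to it. The change is a cheap improvement and should be made.

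**What to change.** In section 2.b, after the sentence on the interview and the contact with the PI, insert:

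> For abuse disclosures, before any parent is notified the PI or covering investigator will establish whom the disclosure concerns. If that person is or may be a parent, guardian, household member or a parent's partner, any required report to authorities will be made first, the person named will not be notified by study staff as a routine step, and which safe caregiver is told, and when, will follow the authorities' guidance and hospital standards. Otherwise the parent will be notified as now. If a participant discloses both abuse by such a person and suicidal or homicidal thoughts, emergency safety steps proceed immediately and this exception governs which caregiver is told. For suicidal or homicidal disclosures without such abuse, the parent is notified as now.

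Add a cross-reference to this text in section 1.c.

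The last two sentences are needed because section 2.b handles all these disclosures alike. Without them, an adolescent who discloses both suicidal thoughts and abuse by a parent would fall under two conflicting rules.

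The cost is one paragraph and one cross-reference. No added staff should be needed, since the PI is already contacted before the parent. The downside is that parent notification will be later in some cases, including some where the parent turns out not to be implicated. The statistical plan does not change.
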